### **8.3 30-day & 270 day Follow-ups**

At 30 days (+/- 7 days) and 270 days (+/- 21 days) the patient shall be contacted by telephone at which time information on cardiovascular medication as well as an assessment of adverse events, angina status and CCS class will be obtained.

Page | 19

**CONFIDENTIAL AND PROPRIETARY:** This document and the information contained there-in may not be reproduced, used or disclosed without written permission from the Principal Investigators.

Version: 11\_dtd02Mar2023

IDE G210030

Effective Date: 3/23/2023

End Date: 2/14/2024

## 8.4 Missed Follow-up

The Investigator(s) will make every attempt to follow the subjects. All subjects will be encouraged by the Investigator(s) to report any address or telephone number changes to the trial site. Subjects will be informed of the importance of completing the scheduled follow-up telephone calls even if they are not experiencing any medical issues. If a subject cannot be reached for a follow-up visit, or misses a scheduled visit, the visit will be recorded as a missed visit as of the date of last attempted contact. The procedure for attempts at contact should be three phone calls made and recorded in the study medical record plus mailing of a registered letter and contact with the General Practitioner, if allowed per patient consent.

Study subjects exit the trial when no additional follow-up visits, procedures, or data collection are required. A subject is exited from the trial in the following instances:

- Is lost-to-follow-up (LTFU)
- Voluntarily withdraws from the trial
- Death (Cause of death, if available, is to be reported)
- Completes last trial follow-up visit
- Investigator withdraws the subject from the trial

Once a subject has exited the trial, no further follow-up contact will be performed. However, if premature study exit has occurred, vital status may be obtained from public records if allowed by country law.

## 8.5 Revascularization, CABG, Death

In the event of revascularization of the target lesion, or coronary artery bypass graft (CABG), every effort should be made to obtain a copy of the procedure notes as well as any accompanying imaging performed. In the event of the subject's death, every effort should be made to obtain a copy of a death summary/death certificate and any treatment notes. Information on the cause of intervention or death will be reported by the investigator(s) and reported in the study electronic data capture system.

Page | 20

**CONFIDENTIAL AND PROPRIETARY:** This document and the information contained there-in may not be reproduced, used or disclosed without written permission from the Principal Investigators.

Version: 11\_dtd02Mar2023

IDE G210030

Effective Date: 3/23/2023

End Date: 2/14/2024

## 9 ENDPOINT ANALYSIS AND STATISTICAL METHODS

### 9.1 Analysis Population

The analysis population is the 60 subjects who were enrolled and randomized to treatment with either rotational atherectomy or rotational atherectomy + cutting balloon atherotomy, regardless of procedure outcome. The analysis population excludes subjects who signed the informed consent but who failed to meet angiographic screening criteria (angiographic screen failures).

### 9.2 Sample Size Rationale

The current study is investigating a novel approach for lesion preparation before stent implantation. As there is limited data available to estimate the expected MSA after rotational atherectomy + cutting balloon atherectomy strategy, no formal sample size calculation was performed. A sample size of 60 patients (total n=60) was chosen for this study. However, a sample size of 60 patients will be powered to detect effect sizes as listed below, given an estimated MSA of  $5.50\text{mm}^2 \pm 2.36\text{mm}^2$ , an equal variance, and a two-sided alpha of 0.05.

Table: Power Calculation

Sample Size	Effect Size (mean difference in MSA)	Power
60	1.6	0.733
60	1.7	0.783
60	1.8	0.828
60	1.9	0.866

### 9.3 Study Endpoint Testing

#### 9.3.1 Primary Endpoint Hypothesis

**Endpoint 1:** Minimal stent area (MSA) at the end of the procedure as assessed by IVUS.

The null and alternate hypotheses for the primary endpoint are

H0: Mean MSARA = Mean MSARA+CBA

HA: Mean MSARA  $\neq$  Mean MSARA+CBA

A 2-sided independent samples Student's t-test will be used with a 2-sided alpha of 0.05 to test for differences in MSA between the control (MSARA) and experimental (MSARA+CBA) groups.

Page | 21

**CONFIDENTIAL AND PROPRIETARY:** This document and the information contained there-in may not be reproduced, used or disclosed without written permission from the Principal Investigators.

Version: 11\_dtd02Mar2023

IDE G210030

Effective Date: 3/23/2023

End Date: 2/14/2024

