### 6.3.1 Inclusion Criteria

A subject who meets ***all the following criteria*** potentially ***may be included*** in the trial:

- 1) Patient (or legal guardian) is  $\geq 18$  years if age and understands the trial requirements and the treatment procedures and provides written informed consent
- 2) Patient undergoing PCI for a *de novo* calcified lesion with planned rotational atherectomy and planned drug-eluting stent implantation of a lesion with target vessel reference diameter  $\geq 2.5$  mm and  $\leq 4.0$  mm, lesion length  $\geq 5$  mm and moderate to severe calcification by angiography
- 3) Patient is eligible for PCI
- 4) Patient is willing and able to comply with all protocol-required follow-up evaluations

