### 6.4.2 SECONDARY ENDPOINTS

- IVUS endpoints will be assessed at the following time points
  - Final IVUS (post Stent and post-dilatation)
    - In-segment Minimum lumen area ( $\text{mm}^2$ ), as assessed by IVUS after stent implantation and (optional) post-dilatation, referenced to the EEM
    - Minimum stent expansion (as defined as MSA  $\text{mm}^2$ ), as assessed by IVUS directly after stent implantation and post-dilatation
    - Mean stent expansion (%) –defined as mean stent area divided by the mean reference lumen area, where reference lumen area will be the average of the proximal and distal 10mm to the stent and/or the reference EEM at the site of MSA
    - Any dissection
    - Any malapposition
  - Pre-stent implantation post RA and CBA or POBA
    - Any dissection
    - Assessment of calcium fracture
- Angiographic endpoints measured in both in-stent, injured and in-segment (defined as injured or stent (whichever is larger) plus 5mm either end as feasible)

Page | 13

---

**CONFIDENTIAL AND PROPRIETARY:** This document and the information contained there-in may not be reproduced, used or disclosed without written permission from the Principal Investigators.

Version: 11\_dtd02Mar2023

IDE G210030

---

- Acute lumen gain (mm)
- Final residual diameter stenosis (%)
- Pre, pre-stent, and final minimum lumen diameter (mm)
- Pre-stent and final dissection type B or greater
- Final perforation (Ellis type  $\geq 2$ )
- Final side branch closure ( $\geq 1.5$ mm)
- Device-related endpoints as defined by any problems related to the devices, including but not limited to: balloon rupture, blade detachments, difficulty in withdrawing/advancing the device, or other device related problems as identified by the investigator.
- Clinical endpoints at 30-day and 270 day follow-up:
  - All-cause death (and further classified as cardiac and non-cardiac)
  - Myocardial infarction (as defined by the SCAI definition and Universal definitions, including peri-procedural myocardial infarction)
  - Target lesion revascularization
  - Target vessel revascularization
  - Stent thrombosis (definite/probable)
  - Major bleeding (BARC 3 or 5)
  - Vascular complications
  - Target Lesion Revascularization
  - Functional status (according to CCS class)

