## 6.5 Screening, Enrollment, and Randomization

All patients who are clinically suitable for treatment with a DES and who meet the study inclusion criteria while not meeting any study exclusion criteria will be approached for inclusion in the study. Subjects who agree to participate will sign an Institutional Review Board (IRB) approved study informed consent and will proceed to the cardiac catheterization lab for further assessment of the angiographic inclusion and exclusion criteria.

If the subject meets all inclusion criteria and does not meet any of the exclusion criteria, randomization will be performed before planned use of rotational atherectomy, but after the guidewire has successfully passed the lesion and the subject will be considered enrolled in the study. Randomization will be an integrated functionality of the EDC.

If the subject fails to meet inclusion/exclusion criteria, s/he will be considered a screening failure and will be excluded from data collection. Treatment of screening failures will then proceed as would occur within the standard of care outside of the study.

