## 7.3 Procedure overview

### 7.3.1 Study flow chart

### 7.3.2 Coronary Angiography

Coronary angiography for off-line QCA analysis will be performed 1) at baseline, 2) after each step of the lesion preparation, and 3) at the end of the procedure. After intracoronary injection of 100-200mcg of nitroglycerine, coronary angiography will be performed in two orthogonal projections aimed to minimize lesion foreshortening and differing at least 30° of rotation. The catheter tip, filled with dye, should be visible for QCA calibration and the lesion should ideally be located in the center of the field of view.

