### 7.3.3 Intravascular Ultrasound Assessment

Intravascular ultrasound assessment for off-line analysis will be performed with the following strategy. The 60Mhz OptiCross™ IVUS catheter (Boston Scientific, Marlborough, MA, USA) using automated pull-back at 1mm/s. The catheter will be advanced at least 5 mm distal to the target lesion.

- 1) at baseline, prior to any intervention, if possible. This IVUS run is optional
- 2) after lesion preparation defined as RA + POBA or RA + CBA, and
- 3) at the end of the procedure. This will be following completion of the interventional procedures per the interventional cardiology investigator.

During the procedure, any additional IVUS runs and assessments deemed clinically indicated by the treating physician to guide the procedure will not be precluded from being performed; these will occur prior to the Final post-angioplasty IVUS run.

Only after the operator deems the procedure to be finished, will the final post angioplasty IVUS run be performed for endpoint assessment. In order to reduce bias, operators will be blinded to the final IVUS run pullback images and no additional stent placement or post dilation is allowed after the Final IVUS run. Blinding will be performed by either turning the IVUS console results away from the primary investigator in the room, or having the primary investigator turn away, if the former is not feasible.

To ensure safety, an unblinded physician will be available at the end of the procedure to review the results of the Final IVUS run for safety signals not present on fluoroscopy. If the unblinded physician has any safety-related concerns, the operator will take immediate actions to ensure the safety of the patient.

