### **10.2 Endpoint Evaluation**

An independent Core Lab will evaluate all study angiograms and all study IVUS runs, and an independent Clinical Events Committee will adjudicate all Endpoint-eligible Serious Adverse Events through the duration of the study.

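### The primary t-test of absolute MSA is valid but ignores pre-treatment vessel size, so some precision is probably left unused; how much depends on an R² that no document gives

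*Combined protocol and SAP*

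**What the plan says.** The primary endpoint (6.4.1) is post-procedural minimum stent area in mm² on the final IVUS run. For its analysis, 9.3.1 states: "A 2-sided independent samples Student's t-test will be used with a 2-sided alpha of 0.05 to test for differences in MSA". Sections 9.3 and 9.4 name no covariate or regression model. On allocation, 6.5 says "Randomization will be an integrated functionality of the EDC" and mentions no stratification.

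The inclusion criteria (6.3.1) require "planned drug-eluting stent implantation of a lesion with target vessel reference diameter" between 2.5 and 4.0 mm. Section 9.2 assumes a mean MSA of 5.50 mm² with SD 2.36 mm², says that "no formal sample size calculation was performed", and tabulates power for 60 patients.

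Two baseline sources of vessel size are described. In 7.3.2: "Coronary angiography for off-line QCA analysis will be performed 1) at baseline"; and in 10.2: "An independent Core Lab will evaluate all study angiograms and all study IVUS runs". The pre-treatment IVUS run, by contrast, is to be done "at baseline, prior to any intervention, if possible. This IVUS run is optional" (7.3.3). The angiographic endpoints in 6.4.2 include a pre-procedure minimum lumen diameter but no baseline reference diameter. Section 10.4 refers to a pre-specified SAP. If that is a separate document, its covariate rules are not visible here.

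**The concern.** A stent in a larger vessel can be expected to have a larger area, whichever arm the patient is in. The eligibility limits alone span a (4.0/2.5)² = 2.56-fold ratio of vessel area, although the enrolled spread will be narrower. With no adjustment and no stratification, whatever part of the MSA variation comes from vessel size stays in the error term of the t-test. It also goes uncorrected if the arms happen to differ in vessel size. The protocol treats vessel size as relevant elsewhere: one secondary endpoint in 6.4.2, mean stent expansion, is indexed to a reference.

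The sample is fixed at 60, so interval width is the quantity at stake. The planned test reaches 80% power only for a difference of 1.74 mm², which is 32% of the assumed mean (1.74/5.50). A pre-treatment covariate is one way to narrow the interval without more patients.

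**Working it through.** **Inputs from the protocol.** N = 60, mean 5.50 mm², SD 2.36 mm², two-sided alpha 0.05 (9.2); 1:1 allocation, so 30 per arm (6.1); diameters 2.5 to 4.0 mm (6.3.1). **Assumed, because no document gives them:** the distribution of enrolled diameters, how strongly MSA follows vessel area, and the error in the measured diameter.

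**Step 1: reproduce the plan.** SE = 2.36 × √(1/30 + 1/30) = 0.609 mm². Noncentral t power with 58 df gives 0.733, 0.783, 0.828 and 0.866 at 1.6, 1.7, 1.8 and 1.9 mm², the same as the table in 9.2. The 80%-power difference is 1.736 mm², and the half-width is 2.002 × 0.609 = 1.22 mm².

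**Step 2: the adjusted test.** With one covariate, SE = 2.36 × √(1 − R²) × √(2/30) × √(1 + 1/56), with 57 df. The last factor allows for estimating the slope. At R² = 0.11, for example, the residual SD is 2.36 × √0.89 = 2.226, and SE = 2.226 × 0.2582 × 1.0089 = 0.580. The half-width is then 1.16 mm² and power at 1.6 mm² is 0.774.

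| R² | Power at 1.6 mm² | 95% CI half-width (mm²) | 80%-power difference (mm²) |
|---|---|---|---|
| Unadjusted t-test | 0.733 | 1.22 | 1.74 |
| 0 | 0.725 | 1.23 | 1.75 |
| 0.012 | 0.730 | 1.22 | 1.74 |
| 0.03 | 0.738 | 1.21 | 1.73 |
| 0.08 | 0.760 | 1.18 | 1.68 |
| 0.11 | 0.774 | 1.16 | 1.65 |
| 0.20 | 0.816 | 1.10 | 1.57 |
| 0.37 | 0.897 | 0.98 | 1.39 |

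Break-even is at R² of about 0.018. From the slope factor alone it would be 1 − 1/(1 + 1/56) = 0.0175; the lost degree of freedom accounts for the rest.

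**Step 3: a range for R².** Let mean MSA rise with D² at a fraction k of strict proportionality, and let the diameter D be measured with error SD e. Then R² = [k × (5.50/E[D²]) × Cov(D, D²)]² / [(Var D + e²) × 2.36²]. For uniform D, E[D²] = 10.75, Var D = 0.1875 and Cov(D, D²) = 2 × 3.25 × 0.1875 = 1.219. With k = 1 and e = 0 this gives (0.6235)² / (0.1875 × 5.570) = 0.372.

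Each cell shows R² for e = 0 and then e = 0.2 mm:

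| Assumed diameters | k = 100% | 70% | 50% | 30% |
|---|---|---|---|---|
| Uniform | 0.372, 0.307 | 0.182, 0.150 | 0.093, 0.077 | 0.034, 0.028 |
| Truncated normal, mean 2.9, SD 0.35 | 0.204, 0.137 | 0.100, 0.067 | 0.051, 0.034 | 0.018, 0.012 |
| Truncated normal, mean 3.1, SD 0.40 | 0.247, 0.182 | 0.121, 0.089 | 0.062, 0.045 | 0.022, 0.016 |

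The median of the 24 is 0.083 (power 0.762, half-width 1.18 mm²). Without the 30% column it is 0.110 (power 0.774, half-width 1.16 mm²). Two scenarios fall below break-even (0.012 and 0.016) and one sits on it (0.018). The 10th-to-90th percentile area ratio under these distributions is 1.65 to 2.11.

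**Step 4: missing covariates.** Suppose 10% of baseline frames were unreadable and those patients were dropped, leaving 27 per arm. At R² = 0.11, SE = 2.226 × √(2/27) × √(1 + 1/50) = 0.612 with 51 df, and power falls to 0.727, below the unadjusted 0.733. Keeping those patients, with the covariate set to the pooled mean, gives 0.769 by simulation.

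**Step 5: simulation check.** With 40,000 trials per setting and a normal covariate, ANCOVA power at 1.6 mm² was 0.724, 0.740, 0.772 and 0.895 for R² of 0, 0.03, 0.11 and 0.37. Type I error was 0.048 to 0.051 for both tests, and 0.049 to 0.051 with pooled-mean substitution.

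**The case against.** The strongest reply is that nothing here is an error. An unadjusted t-test is valid, transparent and a legitimate choice for a 60-patient pilot. The R² range comes from an assumed grid with equal weights, and its median is not an estimate of anything in this trial. Even at the two medians the half-width shrinks by only 3% to 5%, power at 1.6 mm² stays below 80%, and the 80%-power difference is still about 30% of the assumed mean (1.65 to 1.68 mm²). Replacing the primary test in a protocol already at version 11 may invite suspicion of a data-driven choice. A supporting ANCOVA would give the adjusted estimate without that risk. Mean stent expansion already brings vessel size in.

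Much of this stands: the gain is modest, its size is assumed, and the t-test needs no defence. It does not remove the case for adjusting. The trade is lopsided: under one power point at risk, against about three to four at the grid medians. Having the change decided by staff who have not seen MSA by arm, and keeping the t-test, largely answers the late-change worry. The stent-expansion endpoint is a different quantity and does not sharpen the comparison of MSA. An unseen SAP could add covariates, but 9.3.1 itself names the unadjusted test, so the two would then have to be reconciled.

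**Conclusion.** The point holds as a missed gain in efficiency, not as a flaw in validity. The change is recommended, not essential. At the assumed median R² of 0.08 to 0.11, power at 1.6 mm² rises by about three to four points and the half-width falls from 1.22 to 1.18 or 1.16 mm². At R² = 0.20 power reaches 0.816. The top value of 0.37 needs uniform diameters, strict proportionality and an error-free covariate all together. Below R² of about 0.018 there is no gain, and at zero the cost is 0.8 of a point (0.733 to 0.725). Confidence is medium, because the conclusion rests on an R² that the documents do not supply.

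**What to change.** Amend 9.3.1 before any analysis of MSA by arm, with the decision taken by staff who have not seen MSA by arm:

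- **Primary analysis:** ANCOVA of MSA on arm and pre-treatment core-lab QCA reference vessel diameter, two-sided alpha 0.05, reporting the adjusted mean difference with its 95% CI.
- **Supporting analysis:** the unadjusted t-test as now written.
- **Unreadable baseline frame:** set the covariate to the mean of all readable baseline diameters, both arms pooled, so that no randomised patient is dropped for a missing covariate.
- **Covariate source:** not baseline IVUS, because that run is optional.

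If MSA by arm has already been seen, leave the t-test as primary and report the ANCOVA as supporting.

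The cost is an IDE protocol amendment with matching SAP text, one degree of freedom, and one further core-lab measurement (the reference diameter, not listed in 6.4.2) from angiograms that it already evaluates. There is no new patient procedure.

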### **9.3.2 Secondary Endpoint Testing**

Time-to-event analyses using Kaplan Meier methods will be performed for dichotomous clinical secondary endpoint outcomes, event rates in both groups will be compared using the log-rank test.

A 2-sided independent samples Student's t-test will be used with a 2-sided alpha of 0.05 to test for differences in continuous secondary endpoints between the control and experimental groups.

### **9.4 Descriptive Statistics**

Descriptive statistics (arithmetic mean, median as indicated, minimum and maximum and standard deviation) will be calculated for continuous variables. Absolute frequencies and percentages will be obtained for qualitative variables. Summary statistics will be presented according to treatment allocation. 95% Confidence intervals will also be provided.

All statistical tests will be performed with a two-sided alpha of 0.05 and 95% confidence intervals will be presented where applicable, unless otherwise specified.

## **10 METHODS USED TO MINIMISE BIAS**

The following methods are employed to minimize bias in the study:

### **10.1 Inclusion Bias**

All patients eligible for PCI treatment with rotational atherectomy and subsequent DES implantation and who meet the clinical study criteria will be offered participation in the study, pending angiographic assessment of angiographic inclusion/exclusion criteria.

### **10.2 Endpoint Evaluation**

An independent Core Lab will evaluate all study angiograms and all study IVUS runs, and an independent Clinical Events Committee will adjudicate all Endpoint-eligible Serious Adverse Events through the duration of the study.

### **10.3 Reported Data Veracity**

Routine monitoring will be conducted for all reported data according to the study monitoring plan.

Page | 22

**CONFIDENTIAL AND PROPRIETARY:** This document and the information contained there-in may not be reproduced, used or disclosed without written permission from the Principal Investigators.

Version: 11\_dtd02Mar2023

IDE G210030

## 10.4 Avoiding Analysis Bias

Statistical analysis will be conducted according to a pre-specified Statistical Analysis Plan (SAP).

## 11 RISK ASSESSMENT

### 11.1 Potential Risk of the angioplasty and RotaPro procedure

Given subjects enrolled into this protocol will be slated for angioplasty with the use of RotaPro irrespective of trial inclusion the risks associated with such procedures are presented and reviewed with the patient as a part of the standard of care procedural consent process.

### 11.2 Potential Risk of the Wolverine include, but are not limited to:

- Abrupt closure
- Acute myocardial infarction
- Angina or unstable angina
- Arrhythmias, including ventricular fibrillation
- Arteriovenous fistula
- Cardiac tamponade/ pericardial effusion
- Cardiogenic shock
- Cerebrovascular accident/ stroke
- Coronary aneurysm
- Coronary artery bypass grafting surgery
- Coronary artery spasm
- Coronary vessel dissection, perforation, rupture, or injury, possibly requiring surgical repair or intervention
- Death
- Drug reactions, including allergic reaction to contrast medium
- Embolism
- Hemodynamic compromise
- Hemorrhage or hematoma
- Hypo/hypertension
- Infection
- Minor vessel trauma
- Myocardial ischemia
- Percutaneous re-intervention
- Pseudoaneurysm (at vascular access site)
- Pyrogenic reaction
- Renal failure
- Respiratory insufficiency
- Restenosis of the dilated vessel
- Side branch occlusion
- Slow flow/ no reflow
- Thrombosis
- Total occlusion of the coronary artery of bypass
- Transient ischemic attack
- Vasovagal reaction
- Ventricular irritability/ dysfunction
- Vessel trauma requiring surgical repair or intervention
- Volume overload

**CONFIDENTIAL AND PROPRIETARY:** This document and the information contained there-in may not be reproduced, used or disclosed without written permission from the Principal Investigators.

